12.5. Electrocardiogram

A 12-lead Electrocardiogram (ECG) will be performed at the time points specified in [Appendix 1](#) and [Appendix 2](#) and if the patient experienced cardiac symptoms during study drug administration. All scheduled 12-lead ECGs will be performed after the patient has rested quietly for at least 5 minutes. In case of hypersensitivity monitoring, any type of ECG can be performed. The findings of 12-lead ECG will be classified as either “Normal”, “Abnormal, Not Clinically Significant”, or “Abnormal, Clinically Significant”.

The number and percentage of patients will be summarized by treatment group, scheduled visit, in the form of a shift table to detect changes from baseline. All ECG data including hypersensitivity monitoring results will be listed for each patient by treatment group and visit.

12.6. Physical Examination

A physical examination will be performed at Screening, on Day 1 and at EOT visit. The examination will include an assessment of general appearance, head and neck, skin, cardiovascular, respiratory, abdominal, neurological, musculoskeletal, lymphatic systems. The findings of physical examination will be classified as either “Normal”, “Abnormal, Not Clinically Significant”, or “Abnormal, Clinically Significant”.

The number and percentage of patients will be summarized by treatment group, scheduled visit, category, in the form of a shift table to detect changes from baseline. All physical examination data will be listed for each patient by treatment group, visit and category.

12.7. Pregnancy Test

Pregnancy tests consist of serum and urine pregnancy tests. Serum pregnancy test will be performed for female patients with childbearing potential at Screening and EOT visit. The serum pregnancy test samples will be analyzed at the local laboratory. If serum pregnancy test is unavailable, urine pregnancy test can be performed instead. Pregnancy test results will be classified as “Positive”, “Negative”.

All pregnancy test results will be listed for each patient tested by treatment group, visit.

12.8. Radiography

Radiography (chest x-ray and/or chest CT) will be performed at the time points specified in

[Appendix 1](#). Results for radiography will be classified as either “Normal”, “Abnormal, Not Clinically Significant” or “Abnormal, Clinically Significant”.

The number and percentage of patients will be summarized by treatment group, scheduled visit, in the form of a shift table to detect changes from baseline. All radiography results will be listed by treatment group, visit.

12.9. Immunogenicity

Blood samples for immunogenicity assessments will be collected prior to study drug administration on Day 1 and on Days 7, 14, 28, 56, and EOT visit. The immunogenicity of CT-P59 will be assessed by anti-drug antibody (ADA) and neutralizing antibody (NAb) test in validated immunoassay. If the blood sample is unable to be analyzed or is missing at certain time point, some blood samples collected for PK assessment at the same time point can be used for immunogenicity assessment. Additional immunogenicity will be assessed when immune-related AEs occurs. Analysis will be performed at the central laboratory.

The ADA assay will follow a three-tiered approach consisting of (i) screening assay, (ii) specificity/confirmatory assay, and (iii) titration. The test outcome for the screening assay will be either “Potential Positive” or “Negative”. Samples that are “Potential Positive” in the screening assay will be undergone further testing in the specificity/confirmatory assay to determine if patients are a true positive. The test outcome for the specificity/confirmatory assay will be either “Reactive”, “Negative”, or “Not applicable (N/A)”. “Reactive” indicates a true positive test outcome and will be labeled as “Positive” in outputs. “Negative” is considered negative, and “N/A” indicates the assay was negative at the screening phase of the process. Patients with a “Negative” test outcome for either screening or specificity/confirmatory assays will be considered negative for the overall ADA assessment. For further characterization, the antibody level will be assessed by titration in confirmed positive samples.

Samples that are positive in the ADA assay will be analyzed further to conduct a NAb assessment. The test outcome for the screening assay will be either “Positive” or “Negative”.

The number and percentage of patients for the results of the final ADA and the screening NAb assay will be summarized by treatment group, scheduled visit and test.

Descriptive statistics of ADA titer will be displayed by treatment group, scheduled visit and test. The results of ADA titer will also be presented in the listing of immunogenicity results.

All immunogenicity data will be listed for each patient by treatment group and visit.

The first CSR will present only results of ADA screening and confirmatory assay up to Day 14 of each patient.

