The half-lives of the components of CT-P22 and CT-P23, comprising CT-P27, are approximately 17 days and 18 days, respectively. Assuming that the PK of CT-P59 and CT-P27 will be similar, due to the structural similarity between the CT-P27 and the CT-P59, in that an identical human immunoglobulin G1 Fc region backbone, the expected half-life of CT-P59 is 18 days in human.

The further nonclinical results of CT-P59 will be updated in the IB and will serve as the rationale behind dose selection. Safety data from cohort 1 and 2 (10 mg/kg, 20 mg/kg respectively) up to Day 7 in Study CT-P59 1.1 to be conducted in healthy subjects will be submitted for the regulatory's review prior to the dosing of this study, Study CT-P59 1.2, in addition to the nonclinical data. The Data and Safety Monitoring Board (DSMB) members of the healthy and the mild patient studies (Studies CT-P59 1.1 and CT-P59 1.2, respectively) will consist of the same members and the DSMB will be required not to proceed with the dosing of the next cohort in the patient study if there is any safety concern raised in the dose already evaluated in healthy subjects.

CT-P59 will be administrated intravenously. Several human antibodies are approved for IV infusion, which is the same route of administration of CT-P59.

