### 5.2 Treatment Administered

On Day 1, patients who meet all of the inclusion and none of the exclusion criteria will be randomly assigned to one of 2 treatment groups, CT-P59 or placebo, according to randomization scheme. The CT-P59 or placebo will be administered as an IV infusion over 90 minutes ( $\pm 15$  minutes) with SoC (except potential antiviral drugs and/or immune-based therapy under evaluation for treatment of SARS-CoV-2 infection).

Patients in each cohort will receive study drug as follows:

- Cohort 1: CT-P59 20 mg/kg or placebo
- Cohort 2: CT-P59 40 mg/kg or placebo
- Cohort 3: CT-P59 80 mg/kg or placebo

A 250 mL infusion solution of 0.9% weight/volume sodium chloride will be used for patient infusion. The bag will be gently inverted to mix the solution in order to avoid foaming. Parenteral solutions will be inspected visually for particulates and discoloration prior to administration and administration will not be performed if any particulates and discoloration are found. The detailed method about mixing the solution will be described in the pharmacy manual.

When calculating total volume of study drug to be administered, the body weight of each patient measured on Day 1 will be used. Placebo will be administered as in the same volume as the active dose used for CT-P59 in each cohort.

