11.1. Serum Concentrations

Blood samples for PK analyses will be collected from all patients at the time points specified in PK Blood Sampling Time Points and acceptable tolerance windows ([Table 4](#)). If the PK blood sample is unable to be analyzed or is missing at certain time point, some blood samples collected for immunogenicity assessment at the same time point can be used for PK assessment.

Descriptive statistics (n, mean, SD, geometric mean, CV%, minimum, median, and maximum) for serum concentrations will be summarized by CT-P59 treatment groups at each scheduled visit and time point. Individual serum concentrations, collection date/time, and deviations from scheduled time will be listed for the Safety set by CT-P59 treatment groups, visit and time points.

Concentration that are below the lower limit of quantification (BLQ) prior to the study drug administration will be treated as zero (0), and all other BLQ values will be treated as missing for calculation of descriptive statistics of serum PK concentrations and for PK parameter estimation. Measurable concentrations after consecutive BLQs during the terminal phase will also be set to missing.

The mean (\pm SD) serum concentration versus scheduled sample time profiles for the CT-P59 will be presented graphically on both linear and semi-logarithmic scales by CT-P59 treatment groups. In addition, the spaghetti plot of serum concentrations versus scheduled sample time profiles will be presented graphically on both linear and semi-logarithmic scales by CT-P59 treatment groups.

Table 4 Blood Sampling Time Points for Pharmacokinetic Assessment

Day	Time point	Window
Day 1	Predose	Predose within the day
	End of infusion	+ 15 minutes

	1 hour after end of infusion	
Day 2	24 hours after start of infusion	± 1 hour
Day 3	48 hours after start of infusion	
Day 5	96 hours after start of infusion	± 4 hours
Day 7	144 hours after start of infusion	
Day 10	216 hours after start of infusion	
Day 14	312 hours after start of infusion	± 1 day
Day 28	648 hours after start of infusion	± 3 days
Day 56	1,320 hours after start of infusion	± 5 days
Day 90/EOT visit	2,136 hours after start of infusion	

The first CSR will present PK serum concentration results up to Day 14 of each patient.

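### SAP 12.9 accepts an ADA negative whatever the CT-P59 level in the sample, so post-dose negatives in treated patients may be uninterpretable

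*SAP*

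**What the plan says.** SAP 12.9 sets out a three-step ADA assay: screening, confirmation, titration. A negative at either of the first two steps settles the matter, and the patient "will be considered negative for the overall ADA assessment". No concentration limit applies, and the only final outcomes are positive and negative.

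The method is described only as a "test in validated immunoassay". Protocol 6.1.12 says the same, and neither document states a drug-tolerance limit.

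Blood is "collected prior to study drug administration on Day 1 and on Days 7, 14, 28, 56, and EOT visit". Samples positive for ADA go on to the NAb assay; negatives do not. Counts and percentages are tabulated by treatment group and visit. Under SAP 5 the denominator is the number of patients in the group unless otherwise specified. For the earlier report, "The first CSR will present only results of ADA screening and confirmatory assay up to Day 14 of each patient".

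SAP 11.1 (Table 4) and Appendix 1 schedule a PK draw on each of the same days. Individual concentrations are listed, but nothing in the SAP links them to the ADA result. Incidence of ADA and NAb is a secondary safety endpoint (Protocol 2.2.2.4).

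**The concern.** Circulating drug can bind anti-drug antibody and hide it from an immunoassay once its concentration passes the level the assay tolerates. A negative above that level does not show that antibody is absent. The SAP counts it as a true negative and keeps the patient in the denominator, so the error can only lower the reported incidence. Because NAb testing depends on a positive ADA result, a masked ADA also disappears from the NAb table.

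Two features of the schedule make this worth checking. The antibody is long-lived, with only one dose and no scheduled immunogenicity draw after Day 90 (follow-up to Day 180 is by telephone). The first CSR also covers only the visits with the highest drug levels. At stake is whether a low or zero ADA rate can be read as low immunogenicity.

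**Working it through.** The documents state no ADA rate or tolerance, so there is no figure of the plan to reproduce beyond the timing.

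**Inputs.** Half-life: "the expected half-life of CT-P59 is 18 days in human" (Protocol 1.3.2; carried over from CT-P27, not measured). Doses: "Cohort 1: CT-P59 20 mg/kg or placebo" up to "Cohort 3: CT-P59 80 mg/kg or placebo" (Protocol 5.2), a ratio of 80/20 = 4. Last visit: "2,136 hours after start of infusion" (SAP 11.1), which agrees with (90 − 1) × 24 = 2,136 h, or 89 days. Group size: five CT-P59 patients per cohort and three pooled placebo patients.

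**Step 1: drug remaining.** Assume mono-exponential decline: share left = 0.5^((day − 1)/18). For Day 90, 89/18 = 4.94 half-lives. With linear PK and equal half-lives, the levels relative to the initial 20 mg/kg level are:

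| Visit | 20 mg/kg | 40 mg/kg | 80 mg/kg |
|---|---|---|---|
| Day 7 | 79.4% | 159% | 317% |
| Day 14 | 60.6% | 121% | 242% |
| Day 28 | 35.4% | 71% | 141% |
| Day 56 | 12.0% | 24% | 48% |
| Day 90 | 3.2% | 6.5% | 13.0% |

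Over the ±5-day window, the 20 mg/kg Day 90 figure runs from 2.7% to 3.9%. For an assumed half-life of 9 to 24 days, Day 14 is 36.7–68.7% and Day 90 is 0.1–7.7% of each dose's own initial level. A fourfold dose equals a lag of two half-lives, 36 days: 80 mg/kg on Day 90 matches 20 mg/kg on Day 54.

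**Step 2: which negatives could be read.** Let T be the tolerance, as a percentage of the initial 20 mg/kg level. A negative is interpretable where the table entry is at or below T.

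| T (assumed) | 20 mg/kg | 40 mg/kg | 80 mg/kg |
|---|---|---|---|
| 3% | none | none | none |
| 5% | Day 90 | none | none |
| 25% | Days 56, 90 | Days 56, 90 | Day 90 |
| 100% | all five | Days 28–90 | Days 56–90 |
| 320% or more | all five | all five | all five |

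At the two ends no dose gradient arises: either no dose has a readable negative or every dose has. A gradient appears only in between, and only at some visits.

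**Step 3: the same in concentration units.** The documents give no volume of distribution; assume 50–100 mL/kg. Then concentration = dose/volume × 0.5^((day − 1)/18):

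- Day 14: 121–242 µg/mL at 20 mg/kg and 485–970 at 80 mg/kg.
- Day 56: 24–48 and 96–192.
- Day 90: 6.5–13 and 26–52.

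For illustrative tolerances of 10, 50 or 100 µg/mL, every active dose is above tolerance on Day 14, and therefore on Day 7. At 50 µg/mL, Day 56 separates 20 mg/kg (below) from 80 mg/kg (above). At 100 µg/mL, all doses are below on Day 90.

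**Step 4: effect on the endpoint.** One missed case changes a cohort's incidence by 1/5 = 20 points. At an assumed true incidence of 20%, the chance of seeing at least one positive among five is 1 − 0.8^5 = 67.2% with full detection. It is 1 − 0.9^5 = 41.0% if half of cases are detected and 1 − 0.95^5 = 22.6% if a quarter are.

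**The case against.** The best defence is that no bias has been shown. The assay is called validated, and its tolerance would normally sit in laboratory documents that are not part of this set. If the tolerance exceeds the levels reached, the SAP rule is correct as it stands. That is right, and three stronger readings that a reader might infer are not supported:

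- **That every sample contains drug.** The Day 1 sample is predose and placebo patients carry none. Only scheduled post-dose samples of CT-P59 patients are affected.
- **That ADA incidence is biased down.** This depends on the unstated tolerance; only a possible understatement can be claimed.
- **That the understatement grows with dose.** It does so only where the tolerance falls between the groups' levels at a visit. On the illustrative figures all active doses sit on the same side of it at both post-dose visits of the first CSR. The fourfold ratio also assumes linear PK, which SAP 11.2 sets out to estimate.

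It is also fair that the ADA summaries are descriptive, with no test or trend planned, and that five patients per cohort could not support a dose comparison even with a perfect assay. This limits the weight of the point but does not remove it.

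Finally, both listings are in the first CSR (16.2.6.7 for concentrations, 16.2.9.7 for immunogenicity), so a reader could pair 15 treated patients by hand. But the summary table would still count every such sample as negative, and without the tolerance the pairing cannot be interpreted. The first CSR is a declared early cut and the final CSR adds Days 28 to 90, but drug is still expected at Day 90.

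**Conclusion.** The point holds in conditional form. The SAP has a definite classification rule that takes no account of circulating drug, and it gives the reader no means of telling whether a post-dose negative in a CT-P59 patient is informative. If the tolerance is exceeded, ADA incidence and with it NAb incidence may be understated. The size cannot be computed from the documents: depending on the tolerance, anything from none to all of the five scheduled post-dose visits could be affected.

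The conclusion that drug is present rests on the expected 18-day half-life and mono-exponential decline; at 9 days almost none would be left by Day 90. The endpoint is secondary and descriptive, so this is a cheap improvement and does not threaten the trial's primary safety assessment.

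**What to change.** Amend SAP 12.9 as follows:

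1. State the validated drug tolerance of the ADA assay, with its source.
2. Merge the same-visit CT-P59 concentration into the ADA data. Use the reported result, because SAP 11.1 sets post-dose values below quantification to missing for PK summaries. Such a value should count as below tolerance, provided the quantification limit is itself below it.
3. Classify a post-dose ADA-negative sample from a CT-P59 patient as inconclusive when its concentration exceeds the tolerance. Show samples with no paired concentration separately, for example those drawn for an immune-related event.
4. Tabulate positive, negative and inconclusive by treatment group and visit, and list the paired concentration beside each ADA result, in both CSRs. In the NAb table, show inconclusive samples as not tested.

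The cost is SAP wording and one merge. No new scheduled samples are needed, since PK is drawn on every scheduled ADA day and the first CSR already includes concentrations to Day 14. The downside is that fewer samples can be called negative, especially in the first CSR. If the tolerance proves high, nothing is reclassified and the negative results are strengthened.

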12.10. SARS-CoV-2 Infection Related Signs and Symptoms

During the Screening, Treatment Period, and EOT visit, the Investigator or designee will perform a respiratory signs and symptoms assessment (including the examination of ear, nose, throat, sinuses, lungs and other) and assessment for non-respiratory signs and symptoms and/or potential complications of SARS-CoV-2 infection. During the Follow-Up Period, patients will

be asked if they have any SARS-CoV-2 infection related signs and symptoms by telephone call. The assessment will be performed at the scheduled time points specified in [Appendix 1](#) and [Appendix 2](#). The findings of assessment for respiratory signs and symptoms will be classified as either “Normal”, “Abnormal, Not Clinically Significant”, or “Abnormal, Clinically Significant”.

The assessment results for respiratory signs and symptoms at each scheduled visit (excluding follow-up period) with those at baseline will be summarized by treatment group, scheduled visit, category, in the form of a shift table to detect changes from baseline. All assessment data will be listed for each patient by treatment group, visit, assessment type and category.

12.11. Antibody-dependent Enhancement

A patient will be considered to have suspicious Antibody-dependent Enhancement (ADE) if it is checked as “Yes” to “Has the subject experienced any suspicious Antibody-dependent Enhancement (ADE) during the study?” on eCRF.

If a patient has suspicious ADE, additional evaluations will be performed as specified in [Appendix 2](#) during the Treatment Period, EOT, and Follow-Up Period. If symptoms have not resolved or have worsened up to Day 7 after the day of suspicious ADE occurrence, same procedure will be repeated until when the symptoms are resolved and/or no SARS-CoV-2 infection is confirmed by RT-PCT (local).

Proportion of patients with suspicious ADE will be summarized by treatment group.

Additional evaluation results will be listed in each evaluation listing. Only ADE Yes/No data will be listed for each patient by treatment group, separately.

13. Changes in the Planned Analysis

13.1. Changes in the Protocol

1. To use more information in determination of the clinical recovery, ‘at Screening’ was modified to ‘at Baseline’ in the sentence “To satisfy the clinical recovery, symptoms of the moderate or severe in intensity at Screening should be scored as mild or absent, or symptoms of the mild or absent in intensity at Screening should be scored as absent, after study treatment.”.
2. Although ‘Virology analysis vendor (████████████████████)’ conducted an analysis for ‘Cell culture’, statistical analysis was not possible because results were not derived from most of the analysis, so related sentences about ‘Cell culture’ was deleted in the SAP.

14. Reference List

International Council for Harmonisation (ICH) Assembly. ICH E9: Statistical principles for clinical trials – Step 5. 01 September 1998.

US Department of Health and Human Services. (2010). National Institutes of Health, National Cancer Institute. Common Terminology Criteria for Adverse Events (CTCAE) version 5.0. Available from: <http://evs.nci.nih.gov/ftp1/CTCAE/About.html>

15. APPENDIX

Appendix 1: Schedule of Assessments

Study Day (Visit windows)	Screening ¹	Treatment Period												EOT ²	Follow-Up Period ³
	-7 to 1	1	2	3	4	5	6	7	10	14 (±1)	21 (±1)	28 (±3)	56 (±5)	90 (±5)	Bi-weekly up to 180 (±5)
In-house Stay ⁴		X	X	X	(X)	(X)	(X)	(X)							
Telephone Follow-Up Visit															X
Informed consent	X														
Medical history	X														
Demographics	X														
Inclusion/exclusion criteria ⁵	X	X ⁶													
Weight, BMI and height ⁷	X	X ⁶												X	
Physical Examination	X	X ⁶												X	
Urine drug abuse check ⁸	X														
Hepatitis B/C and HIV test ⁹	X														
Serum pregnancy test ¹⁰	X													X	
Clinical laboratory analyses ¹¹	X	X ⁶	X	X		X		X	X	X		X	X	X	
Vital Signs (blood pressure, heart rate, respiratory rate, SpO ₂ and body temperature) ¹²	X	X ⁶	X	X	X ²⁶	X	X ²⁶	X	X	X	X	X	X	X	
12-lead ECG ¹³	X	X ⁶	X					X		X		X	X	X	
Radiography ¹⁴	X			X ²⁶						X					
Randomization		X ⁶													
Administration of study drug ¹⁵		X													
Nasopharyngeal swab ¹⁶															
• RT-PCR (local) ¹⁷	X														
• Viral shedding (central, qPCR and Cell culture)		X ⁶	X	X	X	X	X	X	X	X	X	X			

Study Day (Visit windows)	Screening ¹	Treatment Period													EOT ²	Follow-Up Period ³
	-7 to 1	1	2	3	4	5	6	7	10	14 (±1)	21 (±1)	28 (±3)	56 (±5)	90 (±5)	Bi-weekly up to 180 (±5)	
In-house Stay ⁴		X	X	X	(X)	(X)	(X)	(X)								
Telephone Follow-Up Visit															X	
• Genotyping of SARS-CoV-2 viral isolates (central)		X ⁶	(X) ¹⁸													
Patient diary for SARS-CoV-2 Infection Symptom Checklist ¹⁹	X	X											(X)	(X)		
SARS-CoV-2 infection related signs and symptoms assessment ²⁰	X	X ⁶	X	X		X		X	X	X		X	X	X	X	
Pharmacokinetic sampling ²¹		X	X	X		X		X	X	X		X	X	X		
Immunogenicity sampling		X ⁶						X		X		X	X	X		
Hypersensitivity monitoring ²²		X	X													
Disease status monitoring ²³		X														
Restriction assessment		X														
Prior, concomitant medication ²⁴		X														
Adverse events ²⁵		X														

Abbreviations: ADE=antibody-dependent enhancement; AE=adverse event; ALT=alanine aminotransferase; AST=aspartate aminotransferase; BMI=body mass index; CRP=C-reactive protein; CT=computed tomography; ECG=electrocardiogram; EOT=End-of-Treatment; ESR=erythrocyte sedimentation rate; HBcAb=hepatitis B core antibody, HBsAg=hepatitis B surface antigen; HIV=human immunodeficiency virus; ICF=informed consent form; PK=pharmacokinetic; qPCR= quantitative polymerase chain reaction; RT-PCR=reverse-transcription polymerase chain reaction; SARS-CoV-2=severe acute respiratory syndrome coronavirus 2; SpO₂= peripheral capillary oxygen saturation

1. If Screening visit date and the administration of study drug date (Day 1) are same, all assessments scheduled for the Screening and Day 1 visit can be performed only once on the date before randomization.
2. End-of-Treatment visit assessments will be performed on Day 90. If a patient is early terminated from the study, the patient will be asked to return to the study site for the safety assessments predefined on an EOT visit. If deemed necessary by the investigator, then the patient will be asked to return at the scheduled EOT visit.
3. For all patients, (including a patient who early terminated from the study, if possible) each telephone call follow-up will occur bi-weekly from 2 weeks after the EOT visit to Day 180. During the Follow-Up Period, SARS-CoV-2 infection related signs and symptoms will be assessed by telephone call to capture the suspicious ADE occurrence. For patients with suspicious ADE occurrence, all assessments specified in Table 11-2 (in protocol V1.3) will be conducted on unscheduled visit.
4. All patients will be admitted to the study center on Day 1 and it is recommended to be confined up to Day 7. In-house stay period can be determined by investigator considering the isolation regulation and/or public health capacity of the country, however all patients should be confined to the study center for at least 72 hours (until completion of all assessments on Day 3). After discharge, the consecutive study visits will be carried out on an out-patient basis. During the isolation period according to the regulatory of the country, patients will visit the study center using the transportation provided by Sponsor.

5. Inclusion and exclusion criteria will be confirmed at Screening and on Day 1. If it is concluded that the patients are not eligible in Day 1 assessments, the patients will be considered as Screening failure even if he/she was eligible based on assessments results performed during Screening Period.
6. These assessments should be performed prior to the study drug administration.
7. Measurement of height and BMI will be performed once at Screening.
8. A urine drug tests will be performed at Screening. The screen for drug abuse includes methamphetamine, barbiturates, benzodiazepines, cocaine, tetrahydrocannabinol, and opiates. The urine test can be repeated once at the discretion of the Investigator.
9. At Screening, HBsAg, HBcAb, hepatitis C antibody, HIV-1 or -2 test must be assessed in all patients (mandatory). If HBsAg test result is positive, the patient cannot be enrolled in the study. If HBcAb test is positive, the patient also cannot be enrolled. If hepatitis C antibody, HIV-1 or -2 test result is positive ([Only for protocol V1.3, including country specific A.2], HBsAg, HIV-1 or -2 test result is positive), the patient must be excluded from the study.
10. For female patients with childbearing potential, serum pregnancy test will be performed at Screening and EOT visit. If serum pregnancy test is unavailable, urine pregnancy test can be performed instead. Only patients who are confirmed as nonpregnant can be enrolled in the study.
11. Clinical laboratory testing (clinical chemistry, hematology, and urinalysis) will be performed.

Clinical chemistry	Total protein, serum bilirubin (total, direct), ALT, AST, alkaline phosphatase, γ -glutamyl transferase, blood urea nitrogen, creatinine, creatine kinase, creatine kinase-myocardial band isoenzyme, troponin (I or T, only one applicable), albumin, sodium, potassium, calcium, chloride, inorganic phosphorus, glucose, lactate dehydrogenase, total cholesterol, triglyceride, high-density lipoprotein cholesterol, and CRP
Hematology	Red blood cells, ESR, total white blood cell count, absolute neutrophil count, eosinophil count, lymphocyte count, platelet count, hemoglobin, mean corpuscular volume, mean corpuscular hemoglobin, mean corpuscular hemoglobin concentration, and hematocrit
Urinalysis	Bilirubin, blood, glucose, ketones, leukocytes, nitrite, pH, protein, specific gravity, urobilinogen, and microscopic examination of white blood cell count, red blood cell count, and bacteria

12. Blood pressure, heart rate, respiratory rate, SpO₂ and body temperature will be measured after the patient has rested quietly for at least 5 minutes. SpO₂ will be measured while breathing normal room air. Temperature will be measured using tympanic thermometer throughout the study.
13. All scheduled 12-lead ECGs must be performed after the patient has rested quietly for at least 5 minutes. Regardless of the 12-lead ECG result, further cardiological evaluation can be performed at the Investigator's discretion.
14. Radiography (chest x-ray and/or chest CT) will be performed at the scheduled time point and when the investigator considers it is clinically necessary (e.g., abnormal findings of SpO₂).
15. Study drug will be administered as an IV infusion for 90 minutes (\pm 15 minutes) on Day 1. When calculating total volume of study drug to be administered, the body weight of each patient measured on Day 1 will be used.
16. Nasopharyngeal swabbing will be performed by trained site personnel. A nasopharyngeal swab sampling time points and acceptable tolerance windows are specified in Table 6-2 (in protocol V1.3) and below:
 - Screening: If Screening and administration of study drug occur on the same day, sampling of nasopharyngeal swab will be performed twice both for RT-PCR (local) of Screening and viral shedding and genotype (central) of Day 1, respectively.
 - Day 1: predose (within the day)
 - Day 2: 24 hours (\pm 4 hours) after the start of the study drug infusion.
 - Day 3: 48 hours (\pm 4 hours) after the start of the study drug infusion.
 - Day 4: 72 hours (\pm 4 hours) after the start of the study drug infusion.
 - Day 5: 96 hours (\pm 4 hours) after the start of the study drug infusion.

- Day 6: 120 hours (± 4 hours) after the start of the study drug infusion.
 - Day 7: 144 hours (± 4 hours) after the start of the study drug infusion.
 - Day 10: 216 hours (± 4 hours) after the start of the study drug infusion.
 - Day 21 (± 1 day)
 - Day 14 (± 1 day)
 - Day 28 (± 3 days)
17. If the patient had RT-PCR result confirming SARS-CoV-2 infection prior to obtaining written informed consent (but no more than 7 days from the onset of symptoms), the result can be allowed. During the Screening Period, only one retest for RT-PCR will be allowed, if study drug can be administered no more than 7 days from onset of symptom based on retest results.
18. The genotyping will be performed on samples at time point when resistance is suspected, but not limited to.
19. study drug administration, patients will be instructed to complete the patient diary for SARS-CoV-2 Infection Symptom Checklist twice a day at approximately 12-hour intervals in the morning (between 6 and 10 AM, approximately) and in the evening (between 6 and 10 PM, approximately) from Day 1 until clinical recovery or Day 28, whichever comes first. The patient diary will be recorded once at Screening. On the date of study drug administration (Day 1), the patient diary will be recorded twice before and after the study drug administration. After Day 28, additional recording of the diary will be required if following conditions are met:
- For patients who will achieve clinical recovery at Day 28, patients will record the diary until Day 29 to confirm whether it is maintained at least 24 hours.
 - For patients who will show deterioration (at the discretion of the investigator) after the achievement of clinical recovery, patient will record the diary until secondary achievement of clinical recovery.
 - After Day 28 of regular scheduled study visit, for patients with suspicious ADE occurrence, patient will record the diary for 7 days from the day of suspicious ADE occurrence (specified in Table 11-2 (in protocol V1.3)).
 - However, if patient's condition is not available to record the diary at the discretion of investigator (e.g. sedation state for mechanical ventilator therapy), recording can be discontinued.
20. During the Screening, Treatment Period, and EOT visit, the Investigator or designee will perform a respiratory signs and symptoms assessment (which should include, at a minimum, the examination of ear, nose, throat, sinuses, and lungs) and assessment for potential complications of SARS-CoV-2 infection. During the Follow-Up Period, patients will be asked if they have any SARS-Cov-2 infection related signs and symptoms by telephone call.
21. PK analysis will be performed at the central laboratory. Blood sampling time points and acceptable tolerance windows for PK assessments are specified in Table 6-3 (in protocol V1.3) and below:
- Day 1: predose (within the day), end of infusion (+15 minutes), and 1 hour (+15 minutes) after the end of infusion.
 - Day 2: 24 hours (± 1 hour) after start of infusion.
 - Day 3: 48 hours (± 1 hour) after start of infusion.
 - Day 5: 96 hours (± 4 hours) after start of infusion.
 - Day 7: 144 hours (± 4 hours) after start of infusion.
 - Day 10: 216 hours (± 4 hours) after start of the infusion.
 - Day 14 (± 1 day), Day 28 (± 3 days), Day 56 (± 5 days), and Day 90 (± 5 days)/EOT visit.

22. Hypersensitivity monitoring will be performed at Day 1 predose (within 30 minutes), 15 minutes (±5 minutes), 30 minutes (±5 minutes), 60 minutes (±5 minutes), 90 minutes (±5 minutes), 2 hours (±15 minutes), 3 hours (±15 minutes), 6 hours (±15 minutes), 12 hours (±15 minutes), 24 hours (±30 minutes) from the start of infusion (specified in Table 6-1 (in protocol V1.3)). Vital signs including blood pressure, heart rate, respiratory rate and body temperature will be evaluated for possible hypersensitivity reactions. Any type of ECG will be performed if a patient experiences cardiac symptoms. Emergency equipment, such as adrenaline, antihistamines, corticosteroids, and respiratory support (inhalational therapy, oxygen and artificial ventilator) must be available.
23. Disease status including requirement of supplemental oxygen, intensive care unit transfer, mechanical ventilation use, hospitalization will be monitored during the study period (from signing of ICF to EOT).
24. Prior and/or concomitant medication use will be recorded for the 30 days before the signed date of ICF until the EOT visit.
25. Adverse events will be assessed from the date the ICF is signed until up to EOT visit, regardless of the relationship to the study drug. All incidences of ADE occurring during the follow-up period will be reported as an AE, irrespective of causal relationship.
26. Assessment will be performed according to protocol V1.3, including country specific A.2.

Appendix 2: Schedule of Assessments for Patients with Suspicious ADE Occurrence (Unscheduled Visits)

Evaluation	Suspicious ADE Assessment				
	Day of occurrence ¹	Day 2	Day 3	Day 5	Day 7 ²
Nasopharyngeal swab					
• RT-PCR (local) ³			(X)		
• Viral shedding (central, qPCR and Cell culture)	X	X	X	X	X
• Genotyping of SARS-CoV-2 viral isolates (central) ⁴			(X)		
Patient diary for SARS-CoV-2 Infection Symptom Checklist ⁵			X		
SARS-CoV-2 infection related signs & symptoms assessment ⁶	X	X	X	X	X
Vital Signs ⁷	X	X	X	X	X
12-lead ECG ⁸	X		X		X
Troponin test (I or T, only one applicable)	X		X		X

Abbreviations: ADE=antibody-dependent enhancement; ECG=electrocardiogram; qPCR= quantitative polymerase chain reaction; RT-PCR= reverse-transcription polymerase chain reaction; SARS-CoV-2=severe acute respiratory syndrome coronavirus 2; SpO₂= peripheral capillary oxygen saturation

Note: For suspicious ADE assessment, patients can be hospitalized based on the investigator’s decision. If required, additional assessments can be performed by investigator’s discretion during the hospitalization period. Otherwise, the assessment will be done by out-patient visit. The genotype assessment marked as (X) will be performed in selected visits under the conditions explained in the relevant document of virology analysis.

1. Adverse events will be assessed from the date the ICF is signed until up to EOT visit, regardless of the relationship to the study drug. All incidences of ADE occurring during the follow-up period will be reported as an AE, irrespective of causal relationship.
2. If symptoms have not resolved or have worsened up to Day 7 after the day of suspicious ADE occurrence, same procedure will repeat until when the symptoms are resolved and/or no SARS-CoV-2 infection is confirmed by RT-PCR (local).
3. If required, RT-PCR (local) can be performed at any time by Investigator's discretion.
4. The genotyping will be performed on samples at time point when resistance is suspected, but not limited to.

5. For patients with suspicious ADE occurrence, patient will record the patient diary for SARS-CoV-2 Infection Symptom Checklist for 7 days from the day of suspicious ADE occurrence. Patients will be instructed to complete the diary twice a day at approximately 12-hour intervals in the morning (between 6 and 10 AM, approximately) and in the evening (between 6 and 10 PM, approximately).
6. The Investigator or designee will perform a respiratory signs and symptoms assessment (which should include, at a minimum, the examination of ear, nose, throat, sinuses, and lungs) and assessment for potential complications of SARS-CoV-2 infection.
7. Blood pressure, heart rate, respiratory rate, SpO₂ and body temperature will be measured after the patient has rested quietly for at least 5 minutes. SpO₂ will be measured while breathing normal room air. Temperature will be measured using tympanic thermometer throughout the study.
8. All scheduled 12-lead ECGs must be performed after the patient has rested quietly for at least 5 minutes. Regardless of the 12-lead ECG result, further cardiological evaluation can be performed at the Investigator’s discretion.

